#### 12.6.1.1. Primary Efficacy Endpoint

Weighted sum of pain intensity (SPI) assessments = Area Under the Curve (AUC) of the NRS scores from T0 to T96h at rest ( $AUC_{0\text{ to }96h}$ ).

#### 12.6.1.2. Secondary Efficacy Endpoints

The key secondary endpoints for the comparison of the 4.2 mg CA-008 dose vs. placebo (in descending order of importance):

1. Percentage of subjects who do not require opioids or are opioid free (OF) from T0 to T96):  $OF_{0\text{ to }96h}$
2. Total opioid consumption (in daily oral morphine equivalents) = OC from T0 to T96h:  $OC_{0\text{ to }96h}$
3. Using NRS at rest:  $AUC_{0\text{ to }W1}$

#### 12.6.1.3. Other Efficacy Endpoints

- $AUC_{0\text{ to }24h}$ ,  $AUC_{0\text{ to }120h}$ ,  $AUC_{0\text{ to }W1}$  (walking),  $AUC_{12\text{ to }24h}$ ,  $AUC_{24\text{ to }48h}$ ,  $AUC_{24\text{ to }72h}$ ,  $AUC_{24\text{ to }96h}$ ,  $AUC_{96h\text{ to }120h}$ ,  $AUC_{96h\text{ to }W1}$ ,  $AUC_{24h\text{ to }W1}$ (walking),  $AUC_{96h\text{ to }W2}$ ,  $AUC_{96h\text{ to }W2}$ (walking)
- $OC_{24\text{ to }48h}$ ,  $OC_{24\text{ to }72h}$ ,  $OC_{24\text{ to }96h}$

- OF24 to 96h, OF96h to W1 and OF96h to W2
- TTFRafter T0 and TTFRafter T24h
- Analgesic consumption of OTC analgesics and if prescribed, oxycodone, from T96h to W1 and T96h to W2
- PGE comparing the %age of subjects reporting “poor” + “fair” vs. “good” + “excellent” responses, and the %age reporting each category of response at W1, W2 and W4
- IGE comparing the %age of those reporting “poor” + “fair” vs. “good” + “excellent” responses, and the %age reporting each category at W1, W2 and W4
- Number and %age Subjects with an AE of lack of efficacy (LOE) during the inpatient period: LOE24 to 96h, LOE0 to 96h
- HCU96h to W2 and HCU96h to W4

### 12.6.2. Safety Endpoints

Safety endpoints include the following:

- Incidence of TEAEs and SAEs
- Vital sign measurements
- Physical Exam findings
- Surgical Site assessment findings
- Neurosensory Exam results
- Clinical laboratory test results
- Electrocardiogram (ECG) results
- Concomitant medications

### 12.6.3. Pharmacokinetic Endpoints

#### 12.6.3.1. PK Sampling and Parameters

Based upon the PK results from the Phase 1 bunionectomy ascending dose safety study, the time points for whole blood collection will be at baseline (within the 30 min before the end of study treatment dosing at T0), and at T5min, T10 min, T15min, T30min, T45min, and T1, 1.5, 2, 2.5, 3, 4, 6, 8, 12, 16, and 24h, for a total of 17 samples or approximately 102 mL). Actual sampling times will be used to calculate plasma bupivacaine-derived PK parameters.

A selected number of subjects will participate in the PK study.

The following parameters will be estimated using noncompartmental analysis for CA-008, capsaicin and CA-101:

- Cmax: The maximum measured plasma concentration, obtained directly from the data without interpolation

- $C_{last}$ : Last observed (quantifiable) concentration
- $T_{max}$ : Time of  $C_{max}$
- $t_{1/2}$ : The apparent first-order terminal elimination half-life, calculated as  $0.693/\lambda_z$
- $T_{lag}$ : Time delay between drug administration and first measurable (above lower limit of quantitation) concentration
- $T_{last}$ : Time of occurrence of  $C_{last}$
- $\lambda_z$ : Terminal first-order elimination rate constant
- $AUC_{0-t}$ : Area under the plasma concentration-time curve from time 0 to the last measurable concentration (where time is postdose), calculated by the linear trapezoidal method
- $AUC_{0-\infty}$ : Area under the plasma concentration-time curve, from time of dosing to infinity.
- $AUC_{last}$ : Percentage of the area extrapolated beyond the last quantifiable plasma concentration

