Safety Endpoints:	
The following safety endpoints will be evaluated:
 
 
• Incidence of TEAEs or treatment-emergent SAEs from D0/T0 through D29: Note that all AEs will be recorded from the time the informed consent form (ICF) is signed through D29 (or D36 as applicable). TEAEs are defined as AEs occurring post T0 (end of study treatment infiltration).
 
• Surgical site assessment / wound evaluations to assess for atypical skin reactions, e.g., erythema, pain, pruritus, bruising, swelling, bruising or other skin changes, should be evaluated and graded for severity and followed regularly until resolution or a stable baseline is achieved.
 
• Physical examination (PE) of the lower extremities and vital signs, including neurosensory testing of both lower extremities 
 
○ Note that any observed or reported sensory deficit or clinically significant persistent sensory change remote from the immediate surgical site, such as allodynia or hyperalgesia, must be designated as a neurologic AE. Subjects should be followed until resolution or a stable baseline is achieved.
 
○ Numbness proximal to the incision need not be considered a neurologic AE since this could occur because of tissue trauma and inflammation from the surgery.
 
 
 
• ECG changes from screening to T24h post-treatment
 
• Clinically significant clinical labs changes from screening
 

Pharmacokinetics:	
Approximately 1/3rd of enrolled subjects at each site will participate in the PK study (48 in total; 12 in each treatment group). The PK population will include all subjects who have sufficient concentration-time profiles for estimation of PK parameters.
 
Based upon the PK results from the Phase 1 bunionectomy ascending dose safety study, the time points for whole blood collection will be at baseline (within the 30 min before the start of study treatment dosing), and T5min, T10 min, T15min,

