9. NRS pain assessments during the inpatient stay, at T0.5, 1, 2, 4, 6, 8, 12, 16, 20, 24, and every 4 hours (if awake at time of assessment and if no rescue opioid had been administered in the past 4 hours) until discharge from the inpatient unit. Pain scores may be skipped between the hours of midnight and 6 a.m., but the subject may not miss two consecutive assessments. An additional NRS assessment must be obtained 4 hours (±15 min) after every rescue dose even if this time point occurs between midnight and 6 a.m. The T12, T24, T48, T72 and T96h assessments must be completed even if the subject is asleep at these times. There will be a ±5-minute window allowed for the collection of each assessment in the first 4 hours after the end of surgery, after which will be a ±15-minute window allowed.
10. 2x/day through Day 15
11. Review Subject Diary instructions with subject
12. Dispense Subject Diary
13. Collect Subject Diary Data
14. Dispense no more than 6 tablets of oxycodone 5 mg tablets for use tid prn (although # tablets and refills per investigator discretion).
15. Collect blood samples if subject is participating in the PK study. The time points for collection are at baseline (before dosing), and at T5min, T10 min, T15min, T30min, T45min, and T1, T1.5, T2, T2.5, T3, T4, T6, T8, T12, T16, and T24h (a total of 17 samples). There will be a ±2-minute window allowed for the 5 to 15-minute collections, a ±5-minute window allowed for collections T30 min through T4h, and a ±15-minute window for collections after T4 hours.

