## 9. INVESTIGATIONAL PLAN

### 9.1. Overall Study Design and Plan

This is a Phase 2, multi-center, randomized, double-blind, placebo-controlled, parallel design study evaluating a single dose of one of three CA-008 dose groups vs. placebo injected during an elective BUNX with a multimodal analgesia regimen including an NSAID and regional Mayo block with bupivacaine. The study will be conducted in two parts:

- Inpatient period which continues to 96h after completion of study treatment injection (T0) or T96h.
- Outpatient period which begins on discharge from the inpatient unit through various follow visits to D29±2 (W4) after surgery, or if necessary for ongoing safety assessments, to D36±2 (W5).

Subjects will be undergoing unilateral transpositional first metatarsal osteotomy for the correction of hallux valgus deformity (bunionectomy or BUNX). The surgery is to be performed under light to moderate sedation anesthesia (what constitutes this level of sedation and the additional anesthetic medications used per discretion of the anesthesiologist). In accordance with standard of care, light to moderate sedation will be supplemented with a Mayo block to produce surgical anesthesia and postoperative analgesia. After administering light to moderate sedation, but prior to surgery, perform a Mayo block by infiltrating 0.5% bupivacaine hydrochloride (up to 30 mL total volume, 150 mg) at least 3 cm proximal to the “surgical site”. The Mayo block should be performed at 15-30 minutes prior to study treatment dosing. “Surgical site” is defined as the area extending approximately 2-3 cm in all directions (lateral/medial/proximal/distal) from the incision site and surrounding tissues which may be affected by the infiltration of study treatment.

After the surgery, subjects will be monitored for 96 hours in an inpatient unit. Safety and efficacy evaluations will be performed. After the first week of enrollment, subjects may be enrolled for the pharmacokinetic (PK) portion of the study and have samples drawn prior to CA-008 injection and at various time points over 24h after surgery until the target of 48 PK subjects (12 per treatment group) are enrolled and complete PK assessments. Subjects will be required to meet certain pre-specified criteria prior to discharge.

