### **9.1.2. D-1 or D0: Prior to surgery (baseline) up to the end of surgery**

#### **9.1.2.1. Prior to Surgery**

Subjects who meet the selection criteria at the Screening Visit and are eligible to participate in the study will be required to return to the study center within 45 days of screening. The site may elect to admit the subject to the inpatient unit the evening prior to surgery (D-1) or the day of surgery (D0). The following assessments will be performed:

- Confirm informed consent and eligibility for study participation
- Interim medical and surgical history
- Prior medications
- Interim PE and vital signs as before (include temperature assessment)
- Subject pain assessment training (video only)
- Urine Drug Screening (UDS) and alcohol test (breath or saliva)
- Urine Pregnancy test (FCBP)
- In those subjects participating in the PK study, baseline blood draw for PK analysis prior to surgery (may be done after light to moderate sedation)
- AE Assessment
- Randomize to study treatment

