### 9.1.2.2. Administration of Study treatment

Prior to wound closure, study treatment will be injected/instilled into the soft tissues and osteotomy surgical sites with a total volume of 14 mL of CA-008 or placebo as follows:

- CA-008: 3 doses: 0.7, 2.1 and 4.2 mg in 14 mL volume (concentrations: 0.05, 0.15, 0.3 mg/mL)
- Placebo: CA-008 vehicle (identical to active treatment but without CA-008)

Study treatment will be injected/instilled into the surgical site as follows:

- Instill 2 mL at cut bone sites prior to fixation
- Prior to capsule closure, infiltrate the deep soft tissue and area proximal to the capsule with a total of 9 mL (approximately 2.25 mL into each quadrant circumferentially)
- Close the capsule, but using a small gauge catheter infiltrate 2 mL into the closed capsule space
- Prior to closure of the subcutaneous tissues and skin, instill 1 mL to coat all exposed surfaces of the wound

Note that T0 is the time that the study treatment injection/instillation is completed.

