- Record vital signs: 1, 2, 4, 6, 12, 24 and every 8 hours thereafter (if awake at time of assessment between the hours of 00:00 and 06:00) until discharge from the inpatient unit (may not miss two consecutive assessments). There will be a  $\pm 5$  minute window allowed for the collection of vital signs in the first 4 hours after the end of surgery, after which will be a  $\pm 15$  minute window allowed. Daily temps can be recorded along with vital signs per site SOPs at 1, 2, 4, 6, 12, 24, and every 8 h thereafter until discharge from the inpatient facility (if awake at the time of assessment between hours of midnight and 6 a.m.).
- Perform interim PE: surgical site assessment and neurosensory exam of the foot proximal to the surgical site with contralateral comparison prior to discharge from the inpatient unit.

- Perform ECG: at 24 ( $\pm$ 2) hours after surgery.
- Clinical laboratory tests (chemistry, hematology and urinalysis): at 96 hours prior to discharge from the inpatient unit.
- If the subject is participating in the PK study, obtain whole blood for PK analyses: at baseline (within the 30 min before the start of study treatment dosing), and T5min, T10 min, T15min, T30min, T45min, and T1, T1.5, T2, T2.5, T3, T4, T6, T8, T12, T16, and T24h, for a total of 17 samples).
- Subjects with inadequately controlled pain may request and receive rescue medication at any time; however, subjects will be encouraged to receive rescue only for an NRS  $\geq$  4. Additionally, subjects should be encouraged to wait at least 1 hour after completion of surgery (EOS) before utilizing pain rescue medication, if possible. NRS must be completed within 15 minutes prior to use of pain rescue medication if the time between rescue request and consumption is prolonged.
- Document the time to first use of rescue medication after T0 (between T0 and T24h) and after T24 (between T24h and T96h).
- Document concomitant medication use including doses and times taken
- All AEs that occur from the time a subject's informed consent but prior to study treatment will be captured in the medical history. All AEs and SAEs will be documented and followed from the time of administration of study treatment and will be considered treatment-emergent AEs (TEAEs).

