9 PHARMACOKINETIC EVALUATION

It is anticipated that approximately 1/3rd of enrolled subjects at each site will participate in the PK study (48 in total; 12 in each treatment group).

Blood draws for PK samples will be collected at baseline (within the 30 minutes before the start of study treatment dosing), and at minutes 5, 10, 15, 30, 45, hours 1, 1.5, 2, 2.5, 3, 4, 6, 8, 12, 16, and 24 (a total of 17 samples). Actual sampling times will be used to calculate following plasma bupivacaine-derived PK parameters using noncompartmental analysis for CA-008, capsaicin and CA-101:

- C_{max} : The maximum measured plasma concentration, obtained directly from the data without interpolation
- C_{last} : Last observed (quantifiable) concentration
- T_{max} : Time of C_{max}
- $t_{1/2}$: The apparent first-order terminal elimination half-life, calculated as $0.693/\lambda_z$
- T_{lag} : Time delay between drug administration and first measurable (above lower limit of quantitation) concentration
- T_{last} : Time of occurrence of C_{last}
- λ_z : Terminal first-order elimination rate constant
- AUC_{0-t} : Area under the plasma concentration-time curve from time 0 to the last measurable concentration (where time is post dose), calculated by the linear trapezoidal method
- $AUC_{0-\infty}$: Area under the plasma concentration-time curve, from time of dosing to infinity.
- AUC_{last} : Area under the plasma concentration-time curve, from time of dosing to the time of the last measurable concentration

Sponsor: Concentric Analgesics, Inc.
Protocol Number: CA-PS-201

Statistical Analysis Plan
Date: 09OCT2018

PK concentration data will be listed. There will be a separate PK Analysis Plan that will describe PK analyses.

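### Protocol 12.6.3.1 times the baseline PK sample to the end of dosing, while every other place puts it before dosing starts, so a compliant draw may not be pre-dose

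*Protocol*

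**What the plan says.** The section that defines PK sampling, Protocol 12.6.3.1, places the baseline sample "within the 30 min before the end of study treatment dosing at T0". Protocol 9.1.2.2 fixes what that anchor means: "Note that T0 is the time that the study treatment injection/instillation is completed".

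The other places that time the same sample are:

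- Protocol synopsis, Pharmacokinetics: "within the 30 min before the start of study treatment dosing".
- Protocol 9.1.4: "at baseline (within the 30 min before the start of study treatment dosing".
- SAP 9: "within the 30 minutes before the start of study treatment dosing".
- Protocol Table 1, footnote 15: "The time points for collection are at baseline (before dosing". The table marks the draw in the column for the period before surgery and leaves the surgery column empty.
- Protocol 9.1: PK subjects "have samples drawn prior to CA-008 injection".
- Protocol 9.1.2.1: "baseline blood draw for PK analysis prior to surgery (may be done after light to moderate sedation".

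Three general provisions also bear on the point. The opening of Protocol Section 12 makes Table 1 the schedule for all assessments. Protocol 15.5.5 defines baseline as the last valid value before administration begins, and SAP 3 has a similar definition. Both of those sections also say that a value obtained after dosing is not summarised as a pre-dose value.

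**The concern.** Start and end of dosing are not interchangeable in this trial. Study treatment goes in at four points of the operation, and bone fixation and capsule closure fall between the first instillation and the last. A window that counts back from the end of dosing can therefore open before the first instillation and close after most of the drug is in the wound. A site that follows 12.6.3.1 to the letter could take a sample labelled baseline from a subject who has already received drug.

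The PK profile is a secondary objective. The parameters at risk are the pre-dose concentration, Tlag (the delay from administration to the first measurable concentration) and the early part of AUC, for CA-008, capsaicin and CA-101. A baseline draw taken too late cannot be repeated.

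**Working it through.** **1. The plan's own count.** Protocol 12.6.3.1 states 17 samples and about 102 mL. One baseline + 5 samples at 5, 10, 15, 30 and 45 min + 11 samples at 1, 1.5, 2, 2.5, 3, 4, 6, 8, 12, 16 and 24 h = 17, and 102 / 17 = 6.0 mL each. The count reproduces and includes one baseline, so all the places cited time the same sample.

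**2. The texts side by side.**

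| Place | Anchor for baseline | Allows a draw after the first instillation? |
|---|---|---|
| Protocol 12.6.3.1 | 30 min before end of dosing (T0) | Yes |
| Synopsis, Protocol 9.1.4, SAP 9 | 30 min before start of dosing | No |
| Table 1 footnote 15 | Before dosing | No |
| Protocol 9.1 | Before injection | No |
| Protocol 9.1.2.1, Table 1 column | Before surgery | No |

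The before-surgery and 30-minutes-before-start rules can be met by one draw. Protocol 9.1 puts the Mayo block after sedation, before surgery, and 15 to 30 minutes before study treatment. A draw at or after the block but before incision satisfies both rules. Only 12.6.3.1 stands apart.

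**3. How much drug could precede a compliant draw.** Volumes and concentrations (0.05, 0.15 and 0.30 mg/mL) are from Protocol 9.1.2.2. Dose given so far = cumulative volume × concentration.

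| After stage | Cumulative mL | Share of 14 mL | 0.7 mg arm | 2.1 mg arm | 4.2 mg arm |
|---|---|---|---|---|---|
| Cut bone, 2 mL | 2 | 14.3% | 0.10 mg | 0.30 mg | 0.60 mg |
| Deep tissue, 9 mL | 11 | 78.6% | 0.55 mg | 1.65 mg | 3.30 mg |
| Closed capsule, 2 mL | 13 | 92.9% | 0.65 mg | 1.95 mg | 3.90 mg |
| Before skin closure, 1 mL (T0) | 14 | 100% | 0.70 mg | 2.10 mg | 4.20 mg |

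A draw just before the last stage lies inside the 12.6.3.1 window with up to 13/14 of the dose already given.

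**4. How much of the window is exposed.** Let d be the minutes from first instillation to T0. The share of the 30-minute window that falls after dosing has begun is min(d, 30) / 30. The documents do not give d, so these values are assumptions:

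- d = 5: 5/30 = 17%
- d = 10: 10/30 = 33%
- d = 20: 20/30 = 67%
- d = 30 or more: 100%

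These are shares of the permitted window, not of subjects. The number of subjects affected depends on when sites actually draw.

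**5. Ceiling on subjects.** The plan is for 48 PK subjects, 12 per group. Active arms: 12 × 3 = 36. The 12 placebo subjects receive vehicle without CA-008, so their baseline cannot be altered by study drug.

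**The case against.** The strongest reply is that this is one slip in a plan that is otherwise clear. Table 1 governs assessment timing and puts the draw before surgery, and its footnote says before dosing. Five other places agree with it, and 12.6.3.1 itself still calls the sample a baseline. A site working from Table 1 would not draw after instillation. If one did, the conventions in Protocol 15.5.5 and SAP 3 would keep that value out of pre-dose summaries.

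Most of this stands, and it keeps the point small. It does not remove it. The PK section is where a reader looks for the detail of the window, and it ties the window explicitly to T0, so it cannot be read as meaning the start of dosing. The summary conventions can discard a bad baseline but cannot recover a good one.

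Several stronger readings are tempting, and the documents do not support them:

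- *The plan gives three different baseline times.* The before-surgery and before-start rules are compatible, so there is one outlier.
- *All 48 baselines are at risk.* The placebo samples are not, so the ceiling is 36.
- *The half-life of under 5 minutes in Protocol 7.1.1 shows that such a sample would contain drug.* That figure describes breakdown at neutral pH, illustrated in buffer. It is not a rate of appearance in plasma. A draw after instillation is not pre-dose whatever that rate is, but its effect on measured levels is not documented.
- *The plan has no safeguard in analysis.* For summaries it has one. SAP 9 leaves the PK analyses to a separate PK Analysis Plan, which is not among the documents, so a gap there cannot be assumed.

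**Conclusion.** The baseline window in Protocol 12.6.3.1 is wrong as written. It contradicts the synopsis, Protocol 9.1, 9.1.2.1 and 9.1.4, Table 1 and SAP 9, and it allows a draw that is not pre-dose. The effect is confined to PK: the pre-dose concentration, Tlag and early AUC could be affected in at most 36 active-arm subjects. Reaching 36 would require every active-arm draw to follow 12.6.3.1 instead of Table 1 and to fall after the first instillation. The likely number cannot be derived, because neither the instillation time nor plasma levels during instillation are given. The primary and key secondary efficacy analyses and the sample size are unaffected. This is a minor wording inconsistency, not a chosen design feature. The conclusion rests only on the staged dosing and the definition of T0, both stated in Protocol 9.1.2.2.

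**What to change.** In Protocol 12.6.3.1, replace "within the 30 min before the end of study treatment dosing at T0" with "within the 30 min before the start of study treatment dosing", which is the synopsis wording and agrees with Protocol 9.1.4 and SAP 9. Then confirm that the separate PK Analysis Plan carries over the existing baseline definition, so that a sample drawn after the first instillation is not used as the pre-dose value in the noncompartmental analysis.

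The cost is one phrase in the protocol and one check of the PK plan. The number of draws, the blood volume, the sample size and the efficacy analyses do not change.

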#### **12.6.3.2. Sample Handling:**

Handling and labeling requirements after the collection of each PK sample are described in detail in the Clinical Laboratory Manual.

## 13. ADVERSE EVENTS

### 13.1. Adverse Events and Serious Adverse Events

The following definitions, developed in accordance with the United States (US) Code of Federal Regulations (CFR) and the International Conference on Harmonization (ICH) Clinical Safety Data Management Guidance for Industry, E2A, will be used to identify AEs in this study.

An AE is any untoward medical occurrence in a subject administered a pharmaceutical product that does not necessarily have a causal relationship with this treatment. An AE can therefore be any unfavorable and unintended sign (e.g., including an abnormal laboratory finding), symptom, or increase in severity of a preexisting abnormality, temporally associated with the use of a medicinal (investigational) product, whether or not considered related to the medicinal (investigational) product.

A “suspected adverse reaction” means any AE for which there is a reasonable possibility that the drug caused the event. “Reasonable possibility” means there is evidence to suggest a causal relationship between the drug and the adverse event.

